### **Outcome Measure(s)**

We will measure the number of DLT or BB replacements, time of placement, quality of isolation at 1-hour intervals during the operation, incidence of sore throat and/or hoarseness postoperatively.

### **Analytical Plan**

Results will be analyzed initially using descriptive statistics. Comparison between groups will be done using chi square tests for proportions, and t-tests or ANOVA procedures for continuous variables. Other inferential statistical analysis will be conducted as appropriate.

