The surgeon will be blinded to technique and queried as to the quality of isolation upon entry into the chest and this will be recorded. This will be queried every 60 minutes for the duration of the procedure.

We will record any episodes of loss of isolation and details of repositioning including times and the issue of malposition i.e. the blocker or DLT slipped out or slipped in too far. We will record any episodes of ongoing desaturation which require deflation of the EZ-blocker cuff and/or ventilation of both lungs with a DLT.

We will record the point at which the surgeon the end of OLV. The patient will be extubated according to normal clinical practices and will be taken to the post anesthesia care unit. The Ez-blocker will be removed simultaneously with the ETT. In patients in the EZ-blocker group that remains intubated post procedure the EZ-blocker will be removed prior to going to the ICU. In the DLT group the DLT will be exchanged according to routine clinical practice to a single lumen ETT.

The patient will be contacted on post-operative days 1 and 2 to assessed for hoarseness and sore throat via a VAS scale from 0-100: 0=No sore throat and 100=the worst sore throat imaginable. We will also record any significant morbidity or mortality events such as prolonged mechanical ventilation or cardiac arrest or stroke that may occur within the first 2 post-operative days.

In patients where isolation is troublesome requiring multiple repositioning we will evaluate their preoperative CT scan to determine if there are any anatomical findings on CT which maybe predictive of failure. We will compare these to an equivalent number of control patients from this study population in which isolation was successful. We will attempt to match these patients for size and diagnosis.

The study will be performed at Wake Forest Baptist Medical Center a tertiary academic medical center.

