### **Subjects selection criteria**

Adult patients scheduled for thoracoscopic surgery or thoracotomy requiring lung isolation in which both an EZ-blocker or double lumen tube would be considered an appropriate choice for lung isolation will be recruited.

- Inclusion Criteria**

Patients greater than 18 years of age scheduled for thoracoscopic surgery or thoracotomy requiring lung isolation

Patient presenting as an outpatient for elective thoracic surgery

Inpatients scheduled for thoracic surgery.

- **Exclusion Criteria**

History of difficult airway/intubation  
Patients suspected to have a difficult airway.  
Morbid obesity BMI >39  
Pregnancy  
Emergency status of surgery  
Thoracic surgery requiring a right sided double lumen tube

- **Sample Size**

Assuming a power of 80% and a type 1 error of 5% and a rate of repositioning in the DLT group to be approximately 0.3 repositioning/hour from our experience and a projected rate of repositionings using an EZ-blocker of 0.5 with a standard deviation of 0.3 we estimate a sample size of 36 patients in each arm to demonstrate non-equivalence and so we anticipate enrolling 40 patients in each device in both the left and right sided arm bringing our total enrollment to 160 patients. This is not a multisite study.

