## Appendix 1 Data Sheet

### Data Form for EZ-bronchial Blocker vs. Double Lumen Study

Patient Sticker

ASA:

Weight:      Height:      BMI:

Gender:

Diagnosis:

Laterality:      RIGHT      LEFT

EZ-Blocker      DOUBLE LUMEN

Induction Drug Doses:

Propofol \_\_\_\_\_      Fentanyl \_\_\_\_\_      Rocuronium(0.8mg/kg) \_\_\_\_\_  
Etomidate \_\_\_\_\_

Ventilate/Wait 3 minutes at least.

Begin Blocker or Double Lumen with DL. START TIMING:

Time for placement of EZ-blocker or DLT: \_\_\_\_\_

Number of EZ-blocker or DLT Replacements During Procedure: \_\_\_\_\_

Quality of Isolation: 1- Excellent      2 – Fair      3 - Poor

Time 1 \_\_\_\_\_      Quality of Isolation T1 \_\_\_\_\_

Time 60 min      Quality of Isolation 60 \_\_\_\_\_

Time 120 min      Quality of Isolation 120 \_\_\_\_\_

Time 180 min      Quality of Isolation 180 \_\_\_\_\_

Time 240 min      Quality of Isolation 240 \_\_\_\_\_

Time 300 min      Quality of Isolation 300 \_\_\_\_\_

(Excellent=complete collapse with perfect surgical exposure; Fair=total collapse but the lung has residual air; Poor=no collapse, or partial collapse with interference in surgical exposure)

Incision Time: \_\_\_\_\_      Closure Time: \_\_\_\_\_      Time of OLV \_\_\_\_\_

Sore Throat Post procedure:  
VAS score from page 3

Day 1 \_\_\_\_\_

Day 2 \_\_\_\_\_

Additional Comments/Adverse Events/Other significant intra-operative events

Blocker or Double Lumen Replacement

Replacement Event:	Time	Brief Description of event including duration of replacement event
		Too Deep Too Proximal Other

## Day 1

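### The plan names no analysis suited to the repeated, ordered ratings of isolation quality, and the natural uses of its named tests either inflate false positives or lose power

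*Combined protocol and SAP*

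**What the plan says.** The Objectives section pairs positional stability with quality of lung isolation, for right- and left-sided surgery. Under Design, the surgeon is asked about isolation on entry into the chest, and then "This will be queried every 60 minutes for the duration of the procedure". The Outcome Measure(s) section lists "quality of isolation at 1-hour intervals during the operation" and names no time point or summary.

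The data form in Appendix 1 opens the scale with "Quality of Isolation: 1- Excellent" and continues to 2 (Fair) and 3 (Poor). Its definitions are ordered: "Excellent=complete collapse with perfect surgical exposure; Fair=total collapse but the lung has residual air; Poor=no collapse, or partial collapse with interference in surgical exposure". The form has six slots: a first rating, then 60, 120, 180, 240 and 300 minutes.

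The Analytical Plan is one short paragraph. After descriptive statistics it states: "Comparison between groups will be done using chi square tests for proportions, and t-tests or ANOVA procedures for continuous variables". It then adds: "Other inferential statistical analysis will be conducted as appropriate". Nothing in it refers to isolation quality, to repeated ratings in one patient, or to operations of different length.

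**The concern.** Ratings from the same patient are likely to resemble each other, because anatomy, device position and surgeon persist from one hour to the next. An ordinary chi-square or t-test on all ratings counts one patient several times. Testing each hour separately avoids that but gives several chances of a positive result. It also rests the later comparisons on the longer operations alone, a subset formed after randomization. A chi-square on the three categories makes no use of their order.

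With no rule fixed in advance, the hour or summary could be chosen after the data are seen. A reported difference in isolation quality, or its absence, might then reflect that choice and not the devices.

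**Working it through.** **The plan's own figure.** The only calculation in the documents is for the repositioning rate, starting from "a rate of repositioning in the DLT group to be approximately 0.3 repositioning/hour from our experience" against 0.5 for the EZ-Blocker, with SD 0.3, 80% power and 5% type I error. Two-sided, n = 2 × (1.960 + 0.842)² × 0.3² / 0.2² = 35.3, so 36 per arm, as stated. It does not concern isolation quality, for which the documents give no sample size or error rate.

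**Inputs from the documents.** 40 patients per device per side (Sample Size); three ordered levels and at most six ratings (Appendix 1); nominal level 5%.

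**Inputs assumed.** Excellent/Fair/Poor in 60/30/10%; 2, 3, 4 or 5 ratings per patient with probabilities 0.20, 0.35, 0.30 and 0.15; a latent patient effect that sets the within-patient correlation.

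**False positives with no device difference, one side** (3,000 simulated trials per setting, so a Monte Carlo standard error of √(0.05 × 0.95 / 3000) ≈ 0.4 percentage points near 5%):

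| Use of the tests | Rate |
|---|---|
| Chi-square, all ratings pooled, latent correlation 0.23 | 11% |
| Same, correlation 0.50 | 16% |
| Same, correlation 0.73 | 24% |
| Any significant hour out of four | 16–18% |
| One rank test on each patient's mean rating | 5% |

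A separate latent-normal model with correlations of 0.3 to 0.7 gave about the same results.

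**Hand check on pooling.** The mean number of ratings is 2(0.20) + 3(0.35) + 4(0.30) + 5(0.15) = 3.4, and the mean square is 0.8 + 3.15 + 4.8 + 3.75 = 12.5. The approximate variance inflation is D = 1 + (12.5/3.4 − 1) × ICC = 1 + 2.68 × ICC, with the ICC on the rating scale. For a chi-square with 2 degrees of freedom the actual level is then 0.05^(1/D). Working back, 11% needs D = ln 0.05 / ln 0.11 = 1.36 (ICC 0.13), and 24% needs D = 2.10 (ICC 0.41). Neither ICC is extreme.

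**Hand check on hourly tests.** Four independent tests would give 1 − 0.95⁴ = 18.5%. Correlation between hours lowers this a little, which agrees with 16–18%.

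**Sensitivity.** With 40 or 80 patients per arm, a fixed 2, 3, 4 or 6 ratings each, and latent correlations of 0.3, 0.6 and 0.9, pooling gave 6.5 to 50%. At correlation 0.6 it gave about 10% with 2 ratings and 29 to 31% with 6. Any significant hour gave 8.4 to 26.5%.

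**Valid uses.** Tests on one value per patient kept their level: chi-square at one time point 4.1 to 5.6%, t-test on the patient mean 4.1 to 5.9%, chi-square on the worst rating 3.5 to 5.8%.

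**Power.** With 40 per arm and a device shift of 0.6 latent SD (assumed), a chi-square at a single time point had about 55% power. A rank test on patient means had about 80 to 91%, depending on the correlation. The gap combines two losses, the ordering and the discarded ratings.

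**The case against.** The plan does not say that ratings will be pooled, or that any significant hour will count as a finding. Its last sentence leaves other methods open. The named tests can be applied to one value per patient, and then they hold their level. ANOVA procedures could also be read to include a repeated-measures form, although that would treat a three-level score as continuous. Right and left are separate questions by design.

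Most of this stands, and it rules out four stronger readings that a reader might reach:

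- **That the plan permits only these tests.** It names only these; the open clause allows more.
- **That the analyst must either pool or test every hour.** A single patient-level value is a third course. The plan simply does not choose it.
- **That the tests inflate error two- to sixfold.** The inflation comes from an unstated use of them. Sixfold on this model needs a claim from any one of eight tests, four hours on two sides (30 to 32%), and the documents describe no such rule.
- **That an ordinal scale itself raises false positives.** Ignoring the order costs power; it leaves the type I error alone.

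What does not stand is the open clause as a defence. It permits a sound method without committing to one, so the choice is still free after the data are seen.

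**Conclusion.** The point holds as a gap in pre-specification with a measurable cost. A component of the main objective is a repeated ordered rating, and no named method is matched to it. The natural hourly uses of the named tests are poor. Pooling gives roughly 11 to 24% false positives, and claiming any of four hours gives about 16 to 18% per side. The valid single-time chi-square gives up roughly 25 to 36 percentage points of power (80 − 55 to 91 − 55).

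All of these sizes rest on assumed correlations of about 0.3 to 0.7, 2 to 5 ratings per patient, a 60/30/10 split and, for power, a shift of 0.6 latent SD. The documents give no correlation, rating distribution or case duration, so the figures illustrate what is at stake and do not predict this trial's error rate. The gap itself rests on no assumption. The sample size of 36 per arm is unaffected.

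**What to change.** For this outcome, replace the chi-square with one analysis named in advance: a proportional-odds mixed model, or an ordinal GEE clustered by patient, on all ratings, with device, side, device-by-side and rating time as terms. This uses the ordering and every rating, and it addresses laterality directly.

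A simpler alternative is each patient's mean rating compared by a rank test within each side, with a side-stratified rank test overall. It is not equivalent: it targets a different quantity and gives no device-by-side test.

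The worst rating should not be used unless it is limited to a time window common to all patients, because it rises with case length. With 10% Poor at each rating and, for illustration, independence, the chance of at least one Poor is 1 − 0.9² = 19% with two ratings and 1 − 0.9⁵ = 41% with five. Within-patient correlation narrows this gap but does not remove it.

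Keep the hourly tables as description, without p-values, and show the number of patients still being rated at each hour. The cost is one paragraph in the Analytical Plan and slightly more programming. No new data are needed.

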### **Human Subjects Protection**

### **Subject Recruitment Methods**

Patients will be identified for participation in the Preoperative Assessment Clinic (PAC) prior to the day of surgery or via the OR schedule for patients who are not seen in the PAC. All patients scheduled for elective thoracic surgery pass through the PAC. PAC attendings will be educated by the investigators as to the specific inclusion and exclusion criteria. Patients will be recruited by investigators and/or the study coordinator with the participation and collaboration of PAC attending and other staff present in the clinic involved in this study. We will attempt to recruit qualified subjects in a non-biased manner. Privacy will be protected because subjects will be recruited in the process of a confidential preoperative evaluation in

PAC. If they choose not to participate no research record will be created and as such there will be no contact information to destroy. In house patients will be approached to participate either the night before surgery or on the day of surgery.

### **Informed Consent**

Signed informed consent will be obtained from each subject. Investigators, study coordinator, and PAC attendings involved in the study will obtain informed consent. Inpatients will be interviewed and recruited by either study investigators or other member of the study team.

### **Confidentiality and Privacy**

Confidentiality will be protected by collecting only information needed to assess study outcomes, minimizing to the fullest extent possible the collection of any information that could directly identify subjects, and maintaining all study information in a secure manner. To help ensure subject privacy and confidentiality, only a unique study identifier will appear on the data collection form. Any collected patient identifying information corresponding to the unique study identifier will be maintained on a linkage file, stored separately from the data. The linkage file will be kept secure, with access limited to designated study personnel. Following data collection subject identifying information will be destroyed 4 years after closure of the study via shredding, consistent with data validation and study design, producing an anonymous analytical data set. Data access will be limited to study staff. Data and records will be kept locked and secured, with any computer data password protected. No reference to any individual participant will appear in reports, presentations, or publications that may arise from the study.

### **Data and Safety Monitoring**

The principal investigator will be responsible for the overall monitoring of the data and safety of study participants. The principal investigator will be assisted by other members of the study staff.

### **Reporting of Unanticipated Problems, Adverse Events or Deviations**

Any unanticipated problems, serious and unexpected adverse events, deviations or protocol changes will be promptly reported by the principal investigator or designated member of the research team to the IRB and sponsor or appropriate government agency if appropriate.

## **Appendix**

1. Data collection form

## Appendix 1 Data Sheet

### Data Form for EZ-bronchial Blocker vs. Double Lumen Study

Patient Sticker

ASA:

Weight:      Height:      BMI:

Gender:

Diagnosis:

Laterality:      RIGHT      LEFT

EZ-Blocker      DOUBLE LUMEN

Induction Drug Doses:

Propofol \_\_\_\_\_      Fentanyl \_\_\_\_\_      Rocuronium(0.8mg/kg) \_\_\_\_\_  
Etomidate \_\_\_\_\_

Ventilate/Wait 3 minutes at least.

Begin Blocker or Double Lumen with DL. START TIMING:

Time for placement of EZ-blocker or DLT: \_\_\_\_\_

Number of EZ-blocker or DLT Replacements During Procedure: \_\_\_\_\_

Quality of Isolation: 1- Excellent      2 – Fair      3 - Poor

Time 1 \_\_\_\_\_      Quality of Isolation T1 \_\_\_\_\_

Time 60 min      Quality of Isolation 60 \_\_\_\_\_

Time 120 min      Quality of Isolation 120 \_\_\_\_\_

Time 180 min      Quality of Isolation 180 \_\_\_\_\_

Time 240 min      Quality of Isolation 240 \_\_\_\_\_

Time 300 min      Quality of Isolation 300 \_\_\_\_\_

(Excellent=complete collapse with perfect surgical exposure; Fair=total collapse but the lung has residual air; Poor=no collapse, or partial collapse with interference in surgical exposure)

Incision Time: \_\_\_\_\_      Closure Time: \_\_\_\_\_      Time of OLV \_\_\_\_\_

Sore Throat Post procedure:  
VAS score from page 3

Day 1 \_\_\_\_\_

Day 2 \_\_\_\_\_

Additional Comments/Adverse Events/Other significant intra-operative events

Blocker or Double Lumen Replacement

Replacement Event:	Time	Brief Description of event including duration of replacement event
		Too Deep Too Proximal Other

## Day 1

## No Sore Throat

0

## Worst Sore Throat Imaginable

100

## Day 2

## No Sore Throat

## Worst Sore Throat Imaginable

0

100
